5.4.3.10. Adverse events following first administration/re-initiation of ponesimod

The following TEAEs are flagged for their time of onset:

- TEAEs with onset on Day 1 following first ponesimod administration, i.e., those AEs that start on or after first ponesimod administration start date (on Day 1), by time and date, and before the following calendar date;
- TEAEs with onset on Days 2-7 following first ponesimod administration;
- TEAEs with onset on Days 8-14 following first ponesimod administration;
- TEAEs with onset on Days 15-21 following first ponesimod administration;
- TEAEs with onset on Day 1 following any re-initiation of ponesimod (for definition of a re-initiation, see Section 5.4.1.3).

5.4.3.11. Adverse events ongoing from the core study

Ongoing AEs are those in SDTM202.AE where AECAT = "ONGOING AE FROM AC-058B201".

5.4.3.12. Major adverse cardiovascular events

Based on a pre-defined list of preferred terms belonging to relevant Standardized Medical Dictionary for Regulatory Activities Queries (SMQs), AEs are selected for the major adverse cardiovascular events (MACE) adjudication board evaluation. For each case sent for MACE adjudication, the board members individually assess whether the case is a myocardial infarction, a stroke, or another adverse event. For fatal cases, each member determines whether the death is considered of cardiovascular, non-cardiovascular, or undetermined cause. If not all individual assessments concur, the case is classified into the above listed categories based on a consensus meeting. For data analysis, each case is assigned to one of the following categories:

- cardiovascular death (if a death case is classified as cardiovascular)
- non-fatal myocardial infarction (if the case is classified as myocardial infarction but not as cardiovascular death)
- non-fatal stroke (if the case is classified as stroke but not as cardiovascular death)
- no MACE (if the case is classified as other adverse event, but not as cardiovascular death)

The onset date and treatment-emergent status of a MACE is determined by the onset date and treatment-emergent status of the corresponding AE. In case more than one AE is linked to the same MACE case, the earliest treatment-emergent AE onset date determines the MACE onset date; if none of the linked AE is considered treatment-emergent, the earliest AE onset date determines the

MACE onset date. This may lead to cardiovascular death MACE with an onset date prior to the date of death.

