5.4.4.2. Frequency and AEs per 100 subject-years

AEs are summarized according to both frequency (number of subjects and percentage) and AEs per 100 subject-years (number of events and rate) and based on various grouping terms (for example MedDRA preferred term, or MedDRA primary system organ class).

For frequency of subjects experiencing an AE, AEs reported more than once for a subject with the Analysis Period (based on grouping term) are counted only once per subject.

AEs per 100 subject-years is calculated as (Total cumulative number of events during the Analysis Period / Cumulative observation time over all subjects (years) during the Analysis Period) \times 100, per grouping term. Pregnancy interruptions and events during pregnancy interruptions should be excluded from this calculation.

For total cumulative number of events, multiple records of the same MedDRA preferred term in the AE dataset for the same subject count as individual events (episodes of the same type of event) unless they have the same start date.

The observation time (in days) per subject for summaries of treatment-emergent AEs is calculated as: minimum (date of last administration of ponesimod within the Analysis Period +15, EOS date) – ponesimod start date + 1. Pregnancy interruptions should be excluded from this calculation.

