5.4.4.4. Deaths, other serious adverse events

5.4.4.4.1. Death

The number and percentage of subjects who died are summarized by treatment group, including the reported primary cause of death, for AP3 on the PAS.

All deaths during AP3 are listed on the PAS.

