5.4.4.4.6. MACE

Based on the PAS, treatment emergent MACEs are summarized by presenting, per treatment group, the number and percentage of subjects having any MACE, and having an event of the MACE subcategories (cardiovascular death, non-fatal myocardial infarction, non-fatal stroke. A listing of all events referred to the MACE adjudication committee (whether adjudicated to be MACE or not) is prepared for AP3 on the PAS.

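### Adjudicated MACE is planned only as number and percentage of subjects, despite follow-up from one dose to over 12 years, and a death of undetermined cause has no row in the MACE table

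*SAP*

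**What the plan says.** **Classification.** SAP 5.4.3.12 has the adjudication board decide whether a referred case is a myocardial infarction, a stroke or another event. For fatal cases, "each member determines whether the death is considered of cardiovascular, non-cardiovascular, or undetermined cause". Each case then goes to one of four analysis categories. The first is cardiovascular death. The other three are defined by the absence of that ruling. The infarction category reads "non-fatal myocardial infarction (if the case is classified as myocardial infarction but not as cardiovascular death". The stroke category follows the same pattern, with the same condition and no requirement that the subject survived. Every remaining case falls under the last category, worded "no MACE (if the case is classified as other adverse event, but not as cardiovascular death".

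**Display.** SAP 5.4.4.4.6 presents, per treatment group, "the number and percentage of subjects having any MACE" and the same for the three MACE subcategories. It adds one further output: "A listing of all events referred to the MACE adjudication committee (whether adjudicated to be MACE or not". Deaths are listed, and also tabulated under SAP 5.4.4.4.1, "including the reported primary cause of death".

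**Rates elsewhere.** SAP 5.4.4.2 defines events per 100 subject-years and the denominator: "The observation time (in days) per subject for summaries of treatment-emergent AEs is calculated as" the time from first ponesimod dose to the earlier of last dose plus 15 days and end of study, excluding pregnancy interruptions. Displays using it are planned for treatment-emergent AEs (5.4.4.3.2), SAEs (5.4.4.4.2) and AEs of special interest (5.4.4.4.5).

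**The concern.** There are two separate issues.

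First, the analysis set holds everyone with at least one dose (SAP section 4, Table 1), and the exposure bands in SAP 5.4.1.1 end at more than 12 years. A percentage of subjects pooled over such unequal follow-up grows with time on drug, so it cannot be read as a long-term risk or set against an external rate. Long-term safety is the first objective listed in SAP 1.1, and Protocol 3.2.3 sets up a board specifically for MACE. Its adjudicated result is nevertheless shown only as a crude percentage.

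Second, the board has three possible rulings on a death, but the categories react to only one of them. If a death were ruled undetermined, the MACE table would either carry a fatal case under a 'non-fatal' label or leave it out of the total, and no row would show the board's ruling. With few events expected, one case can matter.

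**Working it through.** The plan states no MACE figure, so there is nothing to reproduce. Three checks apply.

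**1. Mapping under SAP 5.4.3.12.** Three event types by four outcomes give 12 combinations:

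| Event | Not fatal | CV death | Non-CV death | Undetermined death |
|---|---|---|---|---|
| MI | non-fatal MI | CV death | non-fatal MI | non-fatal MI |
| Stroke | non-fatal stroke | CV death | non-fatal stroke | non-fatal stroke |
| Other | no MACE | CV death | no MACE | no MACE |

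Every combination has exactly one category, so the rule is complete. No category requires survival, and none is specific to an undetermined death. An undetermined death with MI or stroke still counts in the any-MACE total; only the label is wrong. An undetermined death with any other event leaves the total altogether. Non-cardiovascular deaths map in the same way.

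**2. Is a MACE rate planned anywhere?** SAP 5.4.4.2 says generally that AEs are summarized by frequency and by rate, but it works through grouping terms. The display types in SAP 5.4.4.3 do not include MACE, and 5.4.4.4.6 names number and percentage only. Cardiovascular events do receive rates by system organ class and preferred term, and through the bradyarrhythmia category of special interest. All of these precede adjudication, and none of the nine special-interest categories in SAP 6.8 covers MI or stroke.

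**3. Scale.**

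*Crude percentage against time on drug.* The formula is 1 − exp(−rate × years). The 4- and 8-year points are the exposure cut points in SAP 5.5.6. The constant rates of 0.1 and 0.5 per 100 subject-years are assumptions, not trial data.

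| Assumed rate per 100 subject-years | 4 years | 8 years | 12 years |
|---|---|---|---|
| 0.1 | 0.40% | 0.80% | 1.19% |
| 0.5 | 1.98% | 3.92% | 5.82% |

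At an unchanged rate, the percentage is 1.98 to 2.00 times higher at 8 years than at 4, and 2.94 to 2.99 times higher at 12 years than at 4.

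*What a rate would look like.* Protocol 1.3.2.4 gives 817 subject-years for the 20 mg group at the interim cut-off of 31 March 2019. The rate is 100 × x / 817. The exact Poisson 95% limits are χ²(0.025; 2x)/2 (zero when x = 0) and χ²(0.975; 2x + 2)/2, each × 100/817. The counts x are assumed:

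| x | Rate per 100 subject-years | 95% CI |
|---|---|---|
| 0 | 0.00 | 0 to 0.45 |
| 1 | 0.12 | 0.003 to 0.68 |
| 2 | 0.24 | 0.03 to 0.88 |
| 3 | 0.37 | 0.08 to 1.07 |

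On this denominator, each undetermined death moved from no MACE into a sensitivity total adds 100/817 = 0.12 per 100 subject-years.

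**The case against.** The case against is substantial, and much of it stands.

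- **The rule is pre-specified and unambiguous.** Protocol 3.2.3 names cardiovascular death, myocardial infarction and stroke among the pre-specified categories. A death not ruled cardiovascular, with no MI or stroke, properly falls outside them. A reader might infer that the MACE definition is incomplete or that two programmers would diverge; the 12-way mapping shows neither. What remains is an inaccurate label and a ruling that no table shows.
- **Such a death is not hidden.** Referred events are listed whether or not they are adjudicated as MACE, and deaths are listed and tabulated. The death table uses the reported cause rather than the adjudicated one, so the listings allow tracing but do not correct the MACE table.
- **Related rates exist.** A reader might infer that fatal events and AEs leading to discontinuation have no exposure-adjusted rate, or that no grouped cardiovascular rate is planned. The documents do not support either inference. SAP 5.4.4.3 puts fatal serious AEs and AEs leading to discontinuation among the overview rows, and 5.4.4.3.2 plans that overview per 100 subject-years. System organ class rates and the bradyarrhythmia category are grouped cardiovascular rates. The gap is confined to adjudicated MACE.
- **A reader could approximate the rate.** SAP 5.4.2.1 reports total subject-years of exposure, and for rare events subject and event counts will be close. That is true, but exposure is not quite the 5.4.4.2 observation time, and no interval would be given.
- **The study is exploratory.** No decision rule depends on this table, and nothing shows a follow-up difference between dose groups that would distort a comparison. This limits the importance of the point but does not make a crude percentage the better summary.
- **The board's charter is not in the documents.** It may contain a convention for undetermined deaths, which cannot be checked.

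**Conclusion.** The point holds in limited form and is one to consider. No rate is planned for adjudicated MACE, while the SAP plans rates for its other main safety groupings over the same unequal follow-up. As the categories are written, an undetermined death would be labelled non-fatal or fall out of the MACE total without a table row to show it.

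The size cannot be stated, because the documents give no count of MACE or of undetermined deaths. If no such death occurred, the classification issue changes no total. The near doubling of the percentage between 4 and 8 years follows simply from doubling the follow-up at an assumed constant rate; it shows why a percentage is hard to interpret, not that this trial's result is biased. The 0.12 per 100 subject-years is a scale for one case in one dose group at the 2019 interim. A reader might go further and infer that the plan conceals cardiovascular deaths; the planned listings and the fatal-SAE overview rows contradict that.

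**What to change.** 1. In SAP 5.4.4.4.6, add treatment-emergent MACE per 100 subject-years, per treatment group, with an exact Poisson 95% confidence interval, using the observation time already defined in 5.4.4.2. Keep the number and percentage of subjects alongside.
2. Keep the main MACE definition in SAP 5.4.3.12. Add one row for adjudicated deaths of undetermined cause, and one sensitivity total that counts them as cardiovascular.
3. Do not label a case with an undetermined death 'non-fatal'. Naming the MI and stroke rows as cases not adjudicated as cardiovascular death is accurate for undetermined and non-cardiovascular deaths alike.
4. If the charter already has a convention for undetermined deaths, cite it in 5.4.3.12.

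The cost is SAP wording and a few table rows. No new data collection is needed, because the board's rulings and the dosing dates already feed planned outputs. The SAP does not name the variable that holds the cause-of-death ruling, so that should be added. The downside for the sponsor is that the MACE figure may become slightly less favourable.

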5.4.4. Analyses of Adverse Events

5.4.4.1. Adverse events

All AEs captured from signature of informed consent up to EOS are reported in the subject listings.

• Unless otherwise specified, all summaries of adverse events are created separately for analysis period AP3, based on the PAS.

Summaries of AEs with onset on Day 1 of ponesimod administration are summarized on the PAS, and with a single column for ponesimod 10 mg (due to the up-titration scheme, all subjects receive ponesimod 10 mg on Day 1 regardless of randomized dose).

Summaries of AEs with onset on Day 1 were presented in the Interim Analysis CSR and are not planned to be presented in the Final CSR.

All summaries of AEs are presented by treatment group, and additionally overall for tables on AP3.

5.4.4.2. Frequency and AEs per 100 subject-years

AEs are summarized according to both frequency (number of subjects and percentage) and AEs per 100 subject-years (number of events and rate) and based on various grouping terms (for example MedDRA preferred term, or MedDRA primary system organ class).

For frequency of subjects experiencing an AE, AEs reported more than once for a subject with the Analysis Period (based on grouping term) are counted only once per subject.

AEs per 100 subject-years is calculated as (Total cumulative number of events during the Analysis Period / Cumulative observation time over all subjects (years) during the Analysis Period) \times 100, per grouping term. Pregnancy interruptions and events during pregnancy interruptions should be excluded from this calculation.

For total cumulative number of events, multiple records of the same MedDRA preferred term in the AE dataset for the same subject count as individual events (episodes of the same type of event) unless they have the same start date.

The observation time (in days) per subject for summaries of treatment-emergent AEs is calculated as: minimum (date of last administration of ponesimod within the Analysis Period +15, EOS date) – ponesimod start date + 1. Pregnancy interruptions should be excluded from this calculation.

5.4.4.3. AE displays

The following types of summary display are used:

- Overview of AEs;
- AEs by primary system organ class (SOC) and preferred term (PT);
- AEs by preferred term (PT);
- AEs by AESI category and PT;
- AEs by maximum intensity and PT.

CONFIDENTIAL – FOIA Exemptions Apply in U.S.

Status: Approved, Date: 20 September 2023

Overview of AE summaries display subjects having any AE, any severe AE, any drug-related AE, any AE leading to study drug discontinuation, any serious AE, any drug-related serious AE, or any fatal serious AE.

AE summaries by grouping term(s) (e.g., SOC, PT, AESI category, maximum intensity) display the number and percentage of subjects having any AE and having an AE in each grouping term. They are sorted by descending frequency of grouping term in the ponesimod 40 mg arm, then the ponesimod 20 mg arm, and finally the ponesimod 10 mg arm. If the frequencies in any grouping term are still the same, alphabetical order is used. Maximum intensity order is fixed as mild, moderate, severe.

5.4.4.3.1. All adverse events

The following summaries are presented:

- Overview of all AEs (frequency) (AP3 only);
- All AEs by SOC and PT (frequency) (AP3 only);

5.4.4.3.2. Treatment-emergent adverse events

The following summaries are presented:

- Overview of TEAEs (frequency);
- Overview of TEAEs (AEs per 100 subject-years);
- Treatment-emergent AEs by SOC and PT (frequency);
- Treatment-emergent AEs with onset on Day 1 of first ponesimod administration, by SOC and PT (frequency) single table with a column for ponesimod 10 mg only;
- Treatment-emergent AEs with onset on Day 1 of any re-initiation by SOC and PT (frequency) (AP3 only, subjects with at least one re-initiation only);
- Treatment-emergent AEs by PT (frequency);
- Treatment-emergent AEs by PT (frequency): PTs occurring only in ≥ 5% subjects in at least one treatment group;
- Treatment-emergent AEs by PT and maximum intensity (frequency);
- Treatment-emergent AEs by SOC and PT (AEs per 100 subject-years);
- Treatment-emergent AEs by PT (AEs per 100 subject-years).

Treatment emergent AEs with onset of Day 1 of first ponesimod or Day 1 of any re-initiation by SOC and PT (frequency) were presented in the Interim Analysis CSR. This was presented in the Interim Analysis CSR and therefore, is not planned to be presented in the Final CSR.

A listing of all AEs is provided for AP3 based on the PAS.

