		• To introduce the 2-week gradual uptitration regimen, to be used in case of re-initiation of study drug during TP3.
		• To amend the guidance for re-initiation of study treatment in the event of study treatment interruption in order to allow patients without the identified cardiovascular risk factors to re-initiate study drug at home.
		• To provide guidance regarding conduct of the study during the COVID-19 (coronavirus) pandemic.
		• To introduce guidance for subject monitoring and discontinuation in case of liver enzyme abnormalities.
		• To align the cardiovascular criteria for discontinuation with that used in Phase 3 clinical studies with ponesimod.

Ponesimod / ACT-128800/ JNJ-67896153 Multiple Sclerosis		EudraCT 2009-011470-15 EDMS-ERI-206617631
Protocol AC-058B202	Confidential	
Version 12		
15 March 2022, page 19/179		

Amendment	Date	Main reason(s)
9 19Oct20		• To inform study sites that the Independent Data Monitoring Committee (IDMC) will be disbanded after the clinical database closure of the last ponesimod double-blind study, in line with the disbandment date agreed per the IDMC Charter.
		• To provide further guidance on study conduct if/when ponesimod becomes commercially available during the study and patients are switched from study drug to commercially available ponesimod.
		• To align the safety reporting procedures with Janssen Safety processes and standards following the integration of Actelion Safety into Janssen Safety.
		• To clarify procedures related to the reporting of multiple sclerosis (MS) relapses and align with the wording in the protocol for the ongoing Phase 3 study (AC-058B303/OPTIMUM-LT).
10	04May21	• To align instructions related to vaccination to those in the Investigator's Brochure.
		• To introduce the transition of paper Case Report Form (CRF) to electronic Case Report Form (eCRF).
		 To further clarify guidance regarding conduct of the study during the COVID-19 (coronavirus) pandemic and the deployment of COVID-19 vaccines. To update sponsor contact information.

EudraCT 2009-011470-15 EDMS-ERI-206617631

Ponesimod / ACT-128800/ JNJ-67896153 Multiple Sclerosis Protocol AC-058B202 Version 12 15 March 2022, page 20/179

Confidential

TITLE	Multicenter, randomized, double-blind, parallel-group extension to study AC-058B201 to investigate the long-term safety, tolerability, and efficacy of 10, 20, and 40 mg/day					

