- In the AC-058B301/OPTIMUM study, the proportion of patients who experienced at least one TEAE was similar in both treatment arms (88.8% and 88.2% of patients in the ponesimod 20 mg and the teriflunomide 14 mg arms, respectively). The most common TEAEs in the ponesimod 20 mg arm were ALT increased (19.5%), nasopharyngitis (19.3%), headache (11.5%) and upper respiratory tract infections (10.6%). Initiation of ponesimod using the gradual uptitration regimen (starting with ponesimod 2 mg) was not associated with clinically significant bradyarrhythmia events; none of reported bradyarrhythmia events were serious or leading to discontinuation of treatment; no second- or higher degree AV blocks were reported.
- In the interim analysis of AC-058B202 (cut-off date of 31 March 2019), long-term treatment with ponesimod was not associated with new safety or tolerability concerns. Study AC-058B202 is ongoing. The results of the interim analysis support the long-term benefit/risk profile of the 20 mg dose as the most optimal dose of ponesimod. Ponesimod 20 mg was shown to be safe and well tolerated in adults with RRMS over long-term treatment of up to 9 years (median exposure to ponesimod in the 20 mg dose group of 8.02 years, corresponding to a total of 817 subject-years).

Ponesimod / ACT-128800 / JNJ-67896153 Multiple Sclerosis		EudraCT 2009-011470-15 EDMS-ERI-206617631
Protocol AC-058B202	Confidential	
Version 12		
15 March 2022, page 48/179		

Nonclinical safety testing of ponesimod indicates an embryotoxic and teratogenic potential. Pregnant or lactating women are excluded from clinical trials, and women of childbearing potential (WOCBP) must use two reliable methods of contraception and must not become pregnant while on study drug and for at least 30 days after study drug discontinuation. A hormonal contraceptive is allowed as one of the required methods of contraception, as the PK profile of hormonal contraceptives has been shown not to be substantially altered in the presence of ponesimod.

More detailed information can be found in the Investigator's Brochure [Ponesimod IB].

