- ≥ 20 mmHg decrease from pre-dose in SBP;
- DBP \leq 50 mmHg or \geq 15 mmHg decrease from pre-dose;
- \geq 15 mmHg decrease from pre-dose in DBP.

Pre-dose values on Day 1, Day 8 and Day 15 following first ponesimod administration and on Day 1 of re-initiation were presented in the Interim Analysis CSR. It was determined that this was no longer required and istherefore not planned to be presented in the Final CSR.

The following summary will be produced for blood pressure abnormalities, as defined above, by treatment group:

• Incidence of treatment-emergent blood pressure abnormalities for SBP and DBP: frequency counts and percentages, where percentages are based on the number of subjects with at least one treatment-emergent post-baseline value during the analysis period (i.e., number of subjects at risk; AP3 on the PAS).

All abnormal blood pressure results are listed by treatment group and visit for AP3 on the PAS.

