- Plot of absolute change from pre-dose values for ECG parameters on nominal Day 1, 8 and 15 relative to first ponesimod administration: mean ± SE by nominal day and nominal timepoint (PAS)*.
- Plot of absolute values for heart rate: mean \pm SE by analysis visit (AP3 on the PAS);
- Plot of absolute change from ponesimod baseline values for heart rate: mean ± SE by analysis visit (AP3 on the PAS).

All abnormal ECG parameter results are listed by treatment group and visit based on the PAS.

Summary tables and plots of ECG parameters on nominal Day 1, 8 and 15 relative to first ponesimod administration were presented in the Interim Analysis CSR and are not planned to be presented in the Final CSR.

Incidence of treatment-emergent abnormalities on nominal Day 1 relative to first ponesimod administration were presented in the Interim Analysis CSR and are not planned to be presented in the Final CSR.

Incidence of treatment-emergent PR and QTc prolongations (including increase from pre-dose) and HR outliers on Day 1 of treatment re-initiation after treatment interruption were presented in the Interim Analysis CSR and are not planned to be presented in the Final CSR.

Clinically relevant morphological ECG findings

The following summaries are produced for morphological ECG findings by treatment group:

- Incidence of clinically relevant morphological ECG findings [as defined above], by preferred term: frequency counts and percentages (AP3 on the PAS);
- Incidence of clinically relevant morphological ECG findings on nominal Day 1, Day 8 and Day 15 relative to first ponesimod administration, by nominal day and preferred term: frequency counts and percentages (PAS)*.

*For summaries/plots on nominal Days 1, 8 and 15 following first ponesimod administration, subjects are summarized as follows:

- For nominal Day 1 all subjects are summarized under ponesimod 10 mg;
- For nominal Day 8 subjects randomized to ponesimod 10 mg are summarized under ponesimod 10 mg, whilst subjects randomized to ponesimod 20 mg or ponesimod 40 mg are summarized under ponesimod 20 mg;
- For nominal Day 15 all subjects are summarized under their randomized dose.

This reflects the up-titration scheme and the doses that subjects were receiving at the time.

Post-dose hourly assessments are not included in summaries/plots by visit.

For tables reporting treatment-emergent abnormalities/findings, all assessments are considered, whether scheduled or unscheduled, pre-or post-dose.

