Bradyarrhythmia occurring post-first dose	Bradyarrhythmias (including conduction defects and disorders of the sinus node function)	Blood pressure ambulatory decreased, Blood pressure decreased, Blood pressure decreased, Blood pressure diastolic decreased, Blood pressure fluctuation, Blood pressure orthostatic decreased, Blood pressure systolic decreased, Bradycardia, Central bradycardia., Chronotropic incompetence, Circulatory collapse, Diastolic hypotension, Electrocardiogram RR interval prolonged, Heart rate decreased, Hypotension, Labile blood pressure, Loss of consciousness, Mean arterial pressure decreased, Orthostatic hypotension, Presyncope, Procedural hypotension, Syncope
Macular edema		Cystoid macular oedema, Diabetic retinal oedema, Macular cyst, Macular hole, Macular oedema, Macular pseudohole, Macular rupture, Papilloedema, Pseudopapilloedema, Retinal oedema
Bronchoconstriction	Asthma/bronchospasm (narrow and broad) Interstitial lung disease (narrow and broad)	
Severe liver injury	Hepatic failure, fibrosis and cirrhosis and other liver damage- related conditions (narrow) Hepatitis, non-infectious (narrow)	

Table 13:AESI, SMQ and PTs

Serious opportunistic infections including PML	Opportunistic infections (narrow)	
Skin cancer	Skin neoplasms malignant and unspecified (narrow and broad)	
Non-skin malignancy	Malignant or unspecified tumours (narrow and broad) excluding the PTs included in the SMQ Skin neoplasms malignant and unspecified (narrow and broad)	
Convulsions	Convulsions (narrow)	
Unexpected neurological or psychiatric symptoms/signs (PRES, ADEM, atypical MS relapses)		Acute disseminated encephalomyelitis, Posterior reversible encephalopathy syndrome, Multiple sclerosis relapse

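### No Final CSR summary isolates restart-day effects under the 2020 re-initiation rules, and the SAP's 10 mg definition would miss restarts that begin at 2 mg

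*SAP*

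**What the plan says.** **Dropped outputs.** SAP 5.4.4.3.2 lists a table of treatment-emergent AEs on Day 1 of any re-initiation and then withdraws it from the Final CSR because the interim report already had it: "Treatment emergent AEs with onset of Day 1 of first ponesimod or Day 1 of any re-initiation by SOC and PT (frequency) were presented". SAP 5.4.5.3.1 does the same for PR and QTc prolongation and heart rate: "HR outliers on Day 1 of treatment re-initiation after treatment interruption were presented in the Interim Analysis CSR and are not planned" for the Final CSR. For blood pressure, SAP 5.4.5.2.1 says of the pre-dose values that those on "Day 1 of re-initiation were presented in the Interim Analysis CSR. It was determined that this was no longer required".

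**Dates.** Protocol 1.3.2.4 dates the interim: "In the interim analysis of AC-058B202 (cut-off date of 31 March 2019), long-term treatment with ponesimod was not associated" with new safety concerns. The protocol's amendment history gives Amendment 8 the date 14 May 2020. Two of its purposes matter here: "To introduce the 2-week gradual uptitration regimen, to be used in case of re-initiation of study drug during TP3", and a change to the restart guidance "to allow patients without the identified cardiovascular risk factors to re-initiate study drug at home".

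**Definition.** SAP 5.4.1.3 requires a drug-log record of up-titration, re-initiation or transition at 10 mg, following more than 3 days of interruption. The Day 1 onset flag in SAP 5.4.3.10 refers back to this definition. SAP 5.4.2.2 keeps counts of re-initiations in the Final CSR.

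**AESI.** SAP 6.8 keeps the category "Bradyarrhythmia occurring post-first dose". Table 13 defines it by one SMQ and a list of preferred terms, including syncope, hypotension and loss of consciousness, without any onset condition. SAP 5.4.4.4.5 summarises it over the treatment-emergent period.

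**The concern.** Protocol 1.3.2.4 calls the effect on heart rate and AV conduction the most prominent safety signal, and describes it as transient, mostly gone 6 to 10 hours after a dose. An output meant to show it has to be tied to the dosing day.

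Earlier reporting is a sound reason to drop an output only if no relevant data have accrued since. That holds for first doses, because every patient had started ponesimod long before the interim. It does not hold for restarts, which continue through TP3 and since 2020 have followed a different scheme, partly outside the clinic. More of them were foreseeable: protocol Appendix 5 requires a restart after four missed days, and Appendix 10 recommends or suggests interruptions of up to 12 weeks when pandemic conditions prevent safety follow-up.

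At stake is whether the final report of a long-term safety study can say anything in aggregate about the day of restart under the rules in force in its last years.

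**Working it through.** No figure in the plan needs reproducing. The check has four parts.

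**1. Dates.**
- Interim cut-off 31 March 2019 to Amendment 8, 14 May 2020: 366 + 44 = 410 days.
- Amendment 8 to SAP approval, 20 September 2023: 3 × 365 + 129 = 1,224 days; 1,224 / 365.25 = 3.35 years.
- Interim cut-off to SAP approval: 410 + 1,224 = 1,634 days, or 4.47 years.

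The interim holds no restart under the Amendment 8 rules. It also holds no restart of any kind from the 410 days before that amendment. Sites needed local approval before changing practice, so 3.35 years is the longest the new rules could have run by SAP approval, not the time they ran at each site.

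**2. The re-initiation rule applied to the dosing table.** Protocol Table 6 gives:

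| Day | 1–2 | 3–4 | 5–6 | 7 | 8 | 9 | 10 | 11 | 12–14 | 15 on |
|---|---|---|---|---|---|---|---|---|---|---|
| mg | 2 | 3 | 4 | 5 | 6 | 7 | 8 | 9 | 10 | 20 |

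The SAP rule needs a 10 mg record that follows more than 3 days off drug. Day 1 follows the gap but is 2 mg. The first 10 mg dose is on Day 12 and follows a 9 mg day. Qualifying records: 0 per Table 6 restart, against 1 (on Day 1) for a restart at 10 mg. If the word for following is read loosely, as any time after the gap, the Day 12 record could qualify, but the flagged Day 1 would then be the twelfth day of dosing. Under neither reading does the flag mark the restart day.

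**3. What is collected and still reported.** Under protocol 3.12.5.3 every restart has AE recording and a pre-dose ECG and blood pressure. Hourly post-dose readings for at least 4 hours are required only with cardiovascular risk factors and are optional otherwise. Protocol 3.12.5.6 lists readings up to 12 hours post-dose for restarts after pregnancy. The Final CSR retains:
- listings of all AEs and AESIs, and of abnormal ECG and blood pressure results by visit;
- incidence of heart-rate, PR, QTc and blood pressure abnormalities, and of morphological ECG findings, with ECG abnormality tables drawing on all assessments, scheduled or not, before or after dosing;
- re-initiation counts, on the definition in part 2.

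None of these summaries separates restart-day findings from the rest of treatment.

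**4. The AESI.** It is shown by category and preferred term, as a frequency and per 100 subject-years. SAP 5.4.4.2 sets the time at risk from first ponesimod to the earlier of last dose + 15 days and end of study, less planned pregnancy interruptions. A syncope in year 8 therefore enters a category named for the first dose. The tables by day that would have placed events in time concern first administration only and are also dropped.

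**The case against.** The strongest reply is that nothing is lost. Restart events are recorded, listed, and included in pooled cardiac tables, and a reader can find them by visit and onset date. The AESI is broken down by preferred term, so bradycardia can be told apart from hypotension. All objectives are exploratory. The protocol cites Phase 3 experience that gradual up-titration at treatment initiation did not produce clinically significant bradyarrhythmia. Restarts may also be few: the protocol discourages interruption, and interruption for planned pregnancy had to be requested by Visit P28.

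Much of this stands, and it rules out stronger readings that a reader might infer. It would be wrong to say that restart effects go unmeasured. Only the post-dose ECG and blood pressure of patients restarting at home may be absent. It would be wrong to call the AESI the only remaining cardiac output, or to say that its rate is divided by all AP3 time. Nor can the amount by which the AESI overstates dosing-day events be quantified, since the documents give neither event counts by onset day nor a number of restarts.

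The reply does not rescue the stated reason for dropping the tables. Listings are not a summary, pooled tables carry no restart denominator, and the Phase 3 results cited concern initiation, not restart in this study or at home. SAP 5.4.5.3 also notes that ECG abnormality criteria changed after the 2019 interim, so the interim ECG tables are a weaker substitute. A Snapshot Analysis of 2022 is mentioned, but its content is not described and it is not given as the reason.

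**Conclusion.** The point holds as a gap in reporting and a faulty analysis definition, not as missing data collection. The Final CSR has no aggregate output for restart day under the Amendment 8 rules, and the reason given for dropping the tables fails by 410 days. Read literally, SAP 5.4.1.3 recognises none of the Table 6 restarts, so restoring the tables alone would leave the new-regimen column empty, and the retained re-initiation counts are too low by however many such restarts occurred. The AESI label does not match its content.

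This assumes that the interim CSR the SAP cites is the one cut on 31 March 2019 and that the drug log records the daily dose at restart. The clinical size is unknown because the number of restarts after May 2020 is not given. The change is worth making before the Final CSR, but no confirmatory conclusion depends on it.

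**What to change.** 1. In SAP 5.4.1.3, define a re-initiation for analysis as the first study-drug record after more than 3 days off drug, whatever the dose, so that the Table 6 start is included. The flag in 5.4.3.10 and the counts in 5.4.2.2 then follow.
2. Keep the re-initiation Day 1 AE table and the Day 1 heart-rate, PR and QTc table in the Final CSR, split by restart regimen. Use the number of restarts as denominator, and for ECG the number of restarts with a post-dose ECG. Add a footnote that under protocol 3.12.5.3 post-dose monitoring is mandatory only for patients with cardiovascular risk factors, and that 3.12.5.6 covers restarts after pregnancy.
3. Show the bradyarrhythmia AESI in two rows, onset on a first-dose or re-initiation Day 1 against all other treatment-emergent onset, or rename the category. Do not widen the window to every up-titration day: in Table 6 the dose changes on Days 3, 5, 7 to 12 and 15, which with Day 1 makes 10 of the first 15 days.
4. Reconcile schedule footnote 12 (protocol Tables 1–4, repeated in SAP 6.13), which describes a TP3 re-initiation with a single step on Day 8, with protocol Table 6.

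The cost is a revised derivation and a few tables whose layouts exist from the interim. Counts may be small, and the ECG table will describe mainly patients monitored on site, a selected group.
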